3.6.1.1.1 Association of Immunogenicity with Exposure, Safety and Efficacy

The safety and efficacy analysis mentioned below will be conducted using the following categories:

- ADA positive participants: Participants with treatment-emergent or treatment-boosted response.
- ADA negative participants: Participants with pre-existing immunoreactivity or negative in the ADA assay at all time points.

Impact of ADA on PK profile

Potential associations between ADA variables (eg, ADA peak titers, neutralizing antibody status, treatment-emergent, persistent, indeterminate and transient response, treatment-boosted) and impact on serum concentration profile of dupilumab may be explored. Plot of serum concentration of functional dupilumab versus visit will be provided by ADA variables for each dupilumab dose group. Individual participant plots of dupilumab concentration according to ADA status will be provided.

Impact of ADA on clinical efficacy endpoints

Associations between the ADA variables (eg, ADA peak titers, neutralizing antibody status, treatment-emergent, persistent, treatment-boosted) and the efficacy endpoints may be explored.

Association of ADA with clinical safety endpoints

Association of safety versus ADA status may be analyzed in the ADA population. The safety assessment may focus on the following events:

- Severe injection site reactions last longer than 24 hours or serious injection site reactions,
- Hypersensitivity reactions (SMQ (20000214) hypersensitivity narrow search confirmed by medical review),
- Anaphylactic reactions (SMQ (20000021) anaphylactic reaction narrow search).

Associations between ADA variables (eg, ADA peak titers, neutralizing antibody status, treatment-emergent, persistent and treatment-boosted) and safety may be explored.

3.6.1.2 Quality of life analyses

Quality of life endpoints analyses are defined in [Section 3.3.1.1](#).

3.6.1.3 Biomarker analyses

Total IgE will be summarized in the safety population. Baseline value will be the last value collected prior to the first IMP.

Descriptive statistics (including number, mean, SD, median, Q1, Q3, min, max) at baseline will be summarized and summary plots (median +/- standard error of the mean) on values at each visit, absolute changes from baseline and percent changes from baseline will be provided for the total IgE by intervention group and visit. Where values are below the lower limit of quantification

(LLOQ), one-half of the LLOQ value will always be used. Values will be expressed with two decimals.

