- n* Hematology will include hemoglobin, hematocrit, platelet count, total white blood cell count, differential count, and total red blood cell count. Serum chemistry will include creatinine, blood urea nitrogen, glucose, lactate dehydrogenase, uric acid, total cholesterol, total protein, albumin, total and direct bilirubin, alanine aminotransferase, aspartate aminotransferase, alkaline phosphatase, electrolytes (sodium, potassium, chloride), bicarbonate, and creatine phosphokinase. Urinalysis will include specific gravity, pH, glucose, ketones, blood, and protein. In case the urine dipstick test result is abnormal, a urine sample should be sent into the central laboratory for microscopic examination.
- o* Blood volume required is in accordance with "Blood sample volumes in child health research" (1). See [Section 8](#) for additional details.
- p* Assessments of severity symptoms (patient report outcome, PRO) includes completion of modified UAS7 questionnaires over 7 consecutive days for CSU participants. The PRO is to be recorded in the e-diary on the same time of the day. Completion of modified UAS7 should be done by the child or parent(s)/caregiver(s)/legal guardian(s) for participants aged 4 years or older; and by parent(s)/caregiver(s) for participants aged less than 4 years.
- q* Quality of life will be assessed through C-DLQI questionnaires in participants ≥ 4 years to < 12 years of age and IDQOL in participants < 4 years of age.
- r* In the event of any SAE, any AE of severe injection site reaction lasting longer than 24 hours, or any AESI of anaphylactic reaction or systemic allergic reaction that is related to IMP and require treatment, PK and ADA samples will be collected at or near the onset of the event for any additional analysis if required or for archival purposes.
- s* For participants assigned to PK Schedule A (determined by IRT system at Visit 2): Weeks 0, 1, 12, 24, 36.
- t* For participants assigned to PK Schedule B (determined by IRT system at Visit 2): Weeks 0, 2, 12, 24, 36.
- u* Biomarker sample collection is mandatory for participants with body weight ≥ 30 kg and optional for participants with body weight ≥ 15 kg and < 30 kg.

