8.6 BIOMARKERS

- Whole blood will be collected to investigate exploratory markers of drug response, disease activity, safety and the Type 2 inflammation pathway. Biomarkers will include serum total IgE. Samples will be collected according to the schedule described in the SoA ([Section 1.3](#)) and as detailed in the study laboratory manual.
- Biomarker blood sampling is mandatory for participants with body weight ≥ 30 kg and optional for participants with body weight > 15 kg and < 30 kg.

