3 STATISTICAL ANALYSES

3.1 GENERAL CONSIDERATIONS

In general, continuous data will be summarized using the number of observations available, mean, standard deviation (SD), median, Q1, Q3, minimum, and maximum. Categorical and ordinal data will be summarized using the count and percentage of participants.

The baseline value is defined as the last available value before the first dose of IMP administration except for efficacy analysis, for which the baseline is defined in [Section 3.3.1.1](#) and [Section 3.3.1.2](#). For participants enrolled but not treated, the baseline value is defined as the last available value before enrollment.

Observation period

The observation period will be divided into 4 segments:

- The **pre-treatment** period is defined as the period up to first IMP administration.
- The **treatment-emergent (TE) period** is defined as the period from the first IMP administration to the last IMP administration +98 days (+112 days for children <30 kg). The treatment-emergent period includes the following 2 periods:
 - The **on-treatment period** is defined as the period from the first IMP administration to the last administration of the IMP +14 days (+28 days for children <30 kg),
 - The **residual treatment period** is defined as the period from the end of the on-treatment period to the end of the treatment-emergent period.
- The **post-treatment period** is defined as the period from the end of the treatment-emergent period.

Unless otherwise specified, analyses will be performed overall and by intervention group:

- 200 mg Q4W
- 300 mg Q4W
- 300 mg Q4W, 600 mg LD
- 200 mg Q2W, 400 mg LD

With the footnote: LD = Loading Dose; Q2W = Every 2 weeks; Q4W = Every 4 weeks.

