4 SAMPLE SIZE DETERMINATION

Approximately 24 participants will be enrolled to study intervention with ≥ 8 participants in each of the 2 weight groups (≥ 5 kg to < 30 kg and ≥ 30 kg to < 60 kg).

The number of participants is based on practical considerations and clinical judgment since this study is a single arm study with the primary endpoint being based on a PK parameter. The study is not powered for hypothesis testing of efficacy endpoints.

Based on the observed variability of PK parameters in pediatric patients with AD, it is expected that a minimum of 8 participants per weight group (≥ 5 kg to < 30 kg and ≥ 30 kg to < 60 kg) and a total of 24 participants is adequate to provide precision in PK parameters for CSU participants aged ≥ 2 years to < 12 years.

Enrollment was stopped after 15 participants after it was determined that drug concentration data from at least 7 participants in each weight group (≥ 5 kg to < 30 kg and ≥ 30 kg to < 60 kg), supplemented with PK data from pediatrics in the EFC16461 safety and efficacy studies, were considered adequate to enable the PK profile of dupilumab in children aged ≥ 2 years to < 12 years with uncontrolled CSU to be characterized.

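### The total IgE plots put standard-error-of-the-mean bars on a median, so the bars do not describe the plotted statistic

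*SAP*

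**What the plan says.** SAP section 3.6.1.3 (Biomarker analyses) specifies for total IgE "summary plots (median +/- standard error of the mean) on values at each visit, absolute changes from baseline and percent changes from baseline", and these "will be provided for the total IgE by intervention group and visit". The same sentence opens with a table: "Descriptive statistics (including number, mean, SD, median, Q1, Q3, min, max) at baseline will be summarized". As worded, that table covers baseline only.

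The general rule in SAP section 3.1 is that "continuous data will be summarized using the number of observations available, mean, standard deviation (SD), median, Q1, Q3, minimum, and maximum". It does not pair the SEM with the median. In SAP section 3.2 (primary PK analysis) the SEM appears in a list of summary statistics, not as a bar around a median.

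On group size, SAP section 4 states: "Enrollment was stopped after 15 participants after it was determined that drug concentration data from at least 7 participants in each weight group". Protocol section 1.3 (footnote u) and section 8.6 make biomarker sampling mandatory from 30 kg and optional from 15 kg up to 30 kg. They provide for none below 15 kg.

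On status, protocol section 8.6 says: "Whole blood will be collected to investigate exploratory markers of drug response, disease activity, safety and the Type 2 inflammation pathway". Protocol section 9.2.7 refers biomarker analyses to a separate plan, which is not among the documents.

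**The concern.** A reader takes an error bar to describe the point it is drawn around, as either its precision or the spread of the data. Median ± SEM does neither. Naming the bar SEM in the figure legend discloses the mismatch but does not remove it.

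The pairing also mixes a robust centre with a non-robust bar. One child with very high IgE hardly moves the median but can dominate the SEM. The symmetric lower bar can then pass a limit that the data cannot pass: zero for values, -100% for percent change.

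Because the table in section 3.6.1.3 is tied to baseline, the plots are the only post-baseline IgE summary that the section names. The general rule in section 3.1 may still produce tables at later visits.

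**Working it through.** The plan gives no figure to reproduce. The mismatch follows from definitions, and the simulations below only illustrate its size.

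**Definition.** SEM = SD/√n estimates the sampling SD of the mean. The sampling SD of the median is a different quantity. For normal data at n = 7, 8 and 15 it is about 1.21, 1.16 and 1.24 times SD/√n (simulated), so the bar is somewhat short even without skew. Median ± SEM then covers the true median in 56%, 58% and 57% of samples, while mean ± SEM covers the true mean in 65%, 65% and 67%.

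**Group sizes (SAP section 4).** With 15 enrolled and at least 7 in each weight group, neither weight group can exceed 15 − 7 = 8. So 200 mg Q2W has at most 8 children, and the three Q4W regimens share at most 8. With optional sampling at 15 to <30 kg, the number per regimen and visit may be lower and is not stated. With no sampling provided below 15 kg, the 200 mg Q4W group may have no IgE data.

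**Simulation.** The assumption, which is not from the documents, is lognormal IgE with median 100 and log-SD 0.5, 1.0 or 1.6. There were 400,000 samples per cell. Ratio = SEM / true SE of the median. The typical ratio uses the median SEM.

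| n | log-SD | True SE of median | Median SEM | Typical ratio | 10th-90th percentile of ratio | Lower bar below 0 |
|---|---|---|---|---|---|---|
| 3 | 0.5 | 36.6 | 24.1 | 0.66 | 0.24-1.46 | 1.6% |
| 3 | 1.0 | 94.9 | 51.7 | 0.54 | 0.15-1.80 | 21.7% |
| 3 | 1.6 | 269.3 | 98.8 | 0.37 | 0.07-2.07 | 43.5% |
| 8 | 0.5 | 21.3 | 18.1 | 0.85 | 0.51-1.42 | 0.01% |
| 8 | 1.0 | 47.8 | 45.9 | 0.96 | 0.44-2.28 | 12.2% |
| 8 | 1.6 | 97.4 | 112.8 | 1.16 | 0.37-4.42 | 50.6% |

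The average SEM is pulled up by rare extreme samples. Its ratios are 0.78, 0.84 and 0.95 at n = 3, and 0.92, 1.23 and 2.13 at n = 8. The bar can therefore be too short or too long.

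**Percent change.** Write percent change as 100(r − 1), with r = post-baseline/baseline. Then median − SEM < −100% is the same event as median(r) − SEM(r) < 0. The last column therefore applies, with log-SD now meaning that of the ratio to baseline. At log-SD 0.3 the probability is 0.01% or less at every n run. The absolute-change plot was not simulated.

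**One child's influence (invented values, n = 7).** Take 40, 60, 80, 100, 130, 170, 250.

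- Mean = 830/7 = 118.6, SD = 72.4, SEM = 72.4/√7 = 27.
- Replace 250 by 2000: mean = 2580/7 = 368.6, SD = 720.7, SEM = 720.7/√7 = 272.
- The median stays at 100. The quartiles stay at 70-150, or 60-170 under another quantile definition.
- The lower bar moves from 100 − 27 = 73 to 100 − 272 = −172, which no concentration can reach.

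**The case against.** The strongest reply is that almost nothing depends on these figures. Total IgE is tied to no objective or endpoint, and protocol section 9.2.4 lists no exploratory endpoint analyses. The Schedule of Activities appears to show only two IgE samples, one early and one at Week 24, so a change plot on the current schedule may carry a single post-baseline point. That stands, and it keeps the point minor.

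The separate biomarker analysis plan might define the figures differently. That is possible and cannot be checked, but the SAP wording would still need correcting.

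The sizes rest on an assumed distribution. With 8 children the typical bar is within about 20% of the right length, and the chance of a bar below zero runs from 0.01% to about 51% depending on the log-SD. Nor do the documents support using these log-SDs for the ratio to baseline. So impossible bar ends are a possibility, not an expectation. The mismatch itself needs no such assumption.

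Finally, other pairings would also be coherent: mean ± SEM (the word median could be a slip), or the median with its own confidence interval. Q1-Q3 shows spread instead of precision. This is a fair choice for the sponsor, but no version of it supports median ± SEM.

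**Conclusion.** The concern holds. As written, all three IgE plots carry error bars that belong to a different statistic. The conclusion that the bars are mismatched rests on definitions alone. The numerical sizes rest on the assumed lognormal shape and log-SD range. Under that range the typical bar is close to the right length with 8 children and too short with 3, while single plots vary widely in both directions.

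This is a minor presentation point. It affects no primary or secondary endpoint, test or decision.

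**What to change.** In SAP section 3.6.1.3, replace the median ± SEM specification with *median and Q1-Q3* for values, absolute changes and percent changes. Overlay individual values where a regimen has only a few children. This follows the section 3.1 default, and because quartiles lie within the observed data, the bars cannot fall below zero or below -100%.

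The cost is one phrase in the SAP and one plotting option, with no new data. The drawback is that with 2 or 3 children Q1-Q3 is little more than the range, hence the individual values.

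If the intention was to show precision, mean ± SEM is internally consistent but remains sensitive to one extreme child. A distribution-free 95% interval for the median is not available for groups of 5 or fewer: minimum to maximum covers the median with probability 1 − 2(1/2)^n, which at n = 5 is 1 − 2/32 = 93.75%. The separate biomarker analysis plan should be aligned with whichever display is chosen.

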3.6.2 Subgroup analyses

Not applicable.

3.7 INTERIM ANALYSES

No interim analyses are planned.

A primary database lock will be performed when all enrolled participants have completed their treatment phase. Final analyses in the CSR will be based on all data collected up to this database lock.

The database will be updated at the end of the study for all participants to include the post-treatment follow-up information and updates for the events previously ongoing at the time of the primary lock. Additional data between this database lock and last participant completing last visit will be summarized in a CSR addendum.

3.8 CHANGES TO PROTOCOL-PLANNED ANALYSES

This section summarizes major statistical changes in the protocol amendment(s).

Table 9 - Major statistical changes in protocol amendment(s)

Amendment Number	Approval Date	Changes	Rationale
Initial Version	30-Mar-2022	-	-
Protocol Amendment 01	31-May-2023	Removed the population with chronic inducible cold urticaria and updated the study title accordingly.	Remove the inclusion of patients with CICU following the results of the Phase 3 study EFC16720, which evaluated the efficacy and safety of dupilumab in adult patients with CICU who remained symptomatic despite the use of H1-antihistamine treatment. This study did not meet the required efficacy endpoints to continue this program, including the development in the pediatric CICU population. Only pediatric participants with chronic spontaneous urticaria will be recruited in this study.
		Deleted secondary objective "To assess the impact of dupilumab on urticaria activity in participants with CICU who remain symptomatic despite the use of H1-antihistamine or appropriate preventive measures" and related endpoints.	These objective, endpoints and footnotes are specific to the chronic inducible cold urticaria patient group that is removed from the PKM16982 protocol.

Amendment Number	Approval Date	Changes	Rationale
		Deleted subsections "10.12.4 Wheal Intensity Likert Scale" and "10.12.5 Acquired Cold Urticaria Severity Index".	These subsections are specific to the chronic inducible cold urticaria patient group that is removed from the PKM16982 protocol.
		Removed "A population PK model will be developed using nonlinear mixed effect modeling to describe the PK profile of dupilumab. Pharmacokinetic parameters will be calculated using the population pharmacokinetic (PopPK) model and summarized using descriptive statistics."	A population PK model may be developed using nonlinear mixed effect modeling to describe the PK profile of dupilumab. The population PK analysis will be reported in a separated document.
		Removed "A PopPK model will be developed using nonlinear mixed effect modeling to describe the PK profile of dupilumab. The following PK parameters will be calculated, using the PopPK model."	
		Removed the Week 4 visit. Visits at Week 1 and Week 2 merged to one visit; that is Visit 3A at Week 1 for half of the participants and Visit 3B at Week 2 for the other half. Visits 6, 7 and 8 are renumbered to 4, 5 and 6, respectively.	To reduce the burden of attending site visits for participants (to avoid missing school and work).
		Decreased the number of PK samplings. Participants will be randomized 1:1 to PK schedule A or B. Decreased the number of blood and urine tests.	To decrease pediatric patient burden by reducing the number of blood and urine tests and volume of blood taken.
		Added "Participants will be randomized by IRT system at randomization visit 1:1 to PK schedule A (Weeks 0, 1, 12, 24, 36) or to PK schedule B (Weeks 0, 2, 12, 24, 36)".	
Not applicable	Not applicable	The "enrolled participants" term will be used (instead of "exposed participants") for the definition of Intent-to-treat, population without trial impact due to COVID-19, Safety, Pharmacokinetic and ADA analysis populations.	
Not applicable	Not applicable	The definition of the TE period was updated in the SAP compared to the TE period in the protocol (addition of "(+112 days for children <30 kg)" in the definition).	

4 SAMPLE SIZE DETERMINATION

Approximately 24 participants will be enrolled to study intervention with ≥ 8 participants in each of the 2 weight groups (≥ 5 kg to < 30 kg and ≥ 30 kg to < 60 kg).

The number of participants is based on practical considerations and clinical judgment since this study is a single arm study with the primary endpoint being based on a PK parameter. The study is not powered for hypothesis testing of efficacy endpoints.

Based on the observed variability of PK parameters in pediatric patients with AD, it is expected that a minimum of 8 participants per weight group (≥ 5 kg to < 30 kg and ≥ 30 kg to < 60 kg) and a total of 24 participants is adequate to provide precision in PK parameters for CSU participants aged ≥ 2 years to < 12 years.

Enrollment was stopped after 15 participants after it was determined that drug concentration data from at least 7 participants in each weight group (≥ 5 kg to < 30 kg and ≥ 30 kg to < 60 kg), supplemented with PK data from pediatrics in the EFC16461 safety and efficacy studies, were considered adequate to enable the PK profile of dupilumab in children aged ≥ 2 years to < 12 years with uncontrolled CSU to be characterized.

5 SUPPORTING DOCUMENTATION

5.1 APPENDIX 1 LIST OF ABBREVIATIONS

AE:	adverse event
AESIs:	adverse events of special interest
ALT:	alanine aminotransferase
AST:	aspartate aminotransferase
C-DLQI:	Children's Dermatology Life Quality Index
CSU:	chronic spontaneous urticaria
EOS:	end of study
HLGT:	high-level group term
HLT:	high level term
HSS7:	hive severity score over 7 days
IDQOL:	Infant's Dermatitis Quality of Life Index
ISS7:	itch severity score over 7 days
LD:	loading dose
LLOQ:	lower limit of quantitation/detection limit
LLT:	lower-level term
MedDRA:	Medical Dictionary For Regulatory Activities
mUAS7:	modified Urticaria Activity Score over 7 days
PCSA:	potentially clinically significant abnormality
PT:	preferred term
Q2W:	every 2 weeks
Q4W:	every 4 weeks
QoL:	quality of life
SAP:	statistical analysis plan
SC:	subcutaneously
SD:	standard deviation
SOC:	system organ class
ULN:	upper limit of normal
ULOQ:	upper limit of quantification
WHO-DD:	World Health Organization-drug dictionary

5.2 APPENDIX 2 PARTICIPANT DISPOSITIONS

The number (%) of participants included in each of the analysis populations listed in [Table 3](#) will be summarized.

Screen failures are defined as participants who consent to participate in the study but are not subsequently enrolled. The number (%) of screen failures and reasons for screen failures will be provided in the screened population.

The number (%) of participants in the following categories will be provided:

- Enrolled participants
- Enrolled but not exposed participants
- Enrolled and exposed participants
- Participants who completed the study treatment period as per protocol
- Participants who did not complete the study treatment period as per protocol and main reason for permanent intervention discontinuation
- Participants who completed the study period as per protocol
- Participants who did not complete the study period as per protocol and main reason for study discontinuation

Reasons for permanent study intervention and study discontinuation “adverse event” and “other reasons” will be split as related versus not related to COVID-19, if applicable.

The number (%) of exposed and not enrolled participants will also be summarized.

In addition, the number (%) of participants screened, screened-failed, enrolled, with permanent intervention discontinuation and with early study discontinuation will be provided by country and site.

Protocol deviations

Critical and major protocol deviations (automatic or manual) will be summarized in the enrolled population as well as displayed separately as related versus not related to COVID-19 if applicable.

5.3 APPENDIX 3 DEMOGRAPHICS AND BASELINE CHARACTERISTICS, PRIOR OR CONCOMITANT MEDICATIONS

Demographics, baseline characteristics, medical surgical history

The following demographics and baseline characteristics, medical and surgical history will be summarized using descriptive statistics in the exposed population.

Demographic and baseline characteristics:

- Age in years as quantitative variable and in categories (≥ 2 to < 6 years, ≥ 6 to < 12 years),
- Gender (Male, Female),
- Ethnic origin (American Indian or Alaska Native, Asian, Black or African American, Native Hawaiian or Other Pacific Islander, White, Not reported, Unknown); if Asian origin (Chinese, Japanese, Asian Indian, Korean, Other, Not Reported, Unknown),
- Hispanic Ethnicity (Hispanic or Latino, not Hispanic or Latino, Not reported, Unknown),
- Weight as quantitative variable and in categories (< 15 , 15 to < 30 , ≥ 30 kg).

Medical and surgical history will be coded to a LLT, PT, HLT, HLGT, and associated primary SOC using the MedDRA version currently in effect at Sanofi at the time of database lock. Medical and surgical history will be presented by primary SOC and PT.

Prior or concomitant medications

All medications will be coded using the World Health Organization-Drug Dictionary (WHO-DD) using the version currently in effect at Sanofi at the time of database lock.

- Prior medications are those the participant received prior to first IMP intake. Prior medications can be discontinued before first administration or can be ongoing during treatment period.
- Concomitant medications are any medications received by the participant concomitantly to the IMP during the treatment-emergent period.
- Post-treatment medications are those the participant received in the period running from the end of the concomitant medications period up to the end of the study.
- A given medication can be classified as a prior medication and/or as a concomitant medication and/or as post-treatment medication. If it cannot be determined whether a given medication was taken prior or concomitantly or post, it will be considered as prior, concomitant, and post-treatment medication.

The prior and concomitant and post-treatment medications will be summarized for the enrolled and exposed population, by anatomic and therapeutic level. Participants will be counted once in each ATC category (anatomic or therapeutic) linked to the medication.

